- Photograph the application site and assess for edema and erythema using the Draize scale, with particular attention to the cannula insertion site.

Period 3. Open-label Treatment

Note: For subjects not meeting the criteria for response at 24 hours, the open-label period will begin after 24 hours of blinded study drug. For subjects meeting the criteria for response at 24 hours, the open-label period will begin after 48 hours of blinded study drug.

At the start of day open-label treatment:

- Using the same procedures for loading and weighing the pump, and confirming cannula deployment as detailed for Day 0, place a new OmniPod® pump containing CSI-Glucagon™ solution (5 mg/mL concentration) and run for 4 hours.
- Basal rate should initially be set at 5 µg/kg/hr with hourly POC glucose measurements and fluid adjustments as per Period 2.
- At 4 hours, remove and the OmniPod® pump and:
 - Photograph the application site, paying particular attention to the cannula insertion site.
 - Assess site for edema and erythema using the Draize scale. Any Draize scores >0 should be followed to resolution, including a follow-up photograph.
- Determine whether, in the investigator's assessment, continued treatment is helpful for clinical care.
 - If yes, and open-label treatment will be continuing, perform "real-world" pump change-out procedure (see Section 9.3.3).
 - If no, and open label treatment is ending, remove CGM and draw blood for immunogenicity testing, plasma insulin and glucagon levels as well as CBC and CMP. Do not perform the "real-world" pump change-out procedure in this case.
- If yes, therapy may continue, including intermittently should procedures, e.g., PET scan, require temporary discontinuation, for up to a cumulative 28 days of glucagon exposure.

- A new OmniPod® pump containing CSI-Glucagon™ solution should be placed at least every 72 hours. The procedures for loading and weighing the pump and confirming successful cannula deployment should be followed each time a new pump is placed.
 - Each time a pump is replaced, determine safety of pump switch out procedures as assessed by occurrence of blood glucose < 50 mg/dL.
 - Each time a pump is removed, including at final termination of therapy, it should be weighed to the nearest whole mg, and the placement site should be photographed and assessed with Draize scales.
 - At least 2 hours prior to each planned pump change, confirm the CGM sensor is working and place another as needed.

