7.2. Interruption and Termination of Dosing

Dosing may be paused at an investigator’s discretion for any serious adverse event (SAE) which occurs in a patient receiving treatment until causality is fully assessed by the Investigator (see Section 12.6). Dosing will be discontinued if the SAE is determined to be probably drug-related, but otherwise may continue (or resume) at the discretion of the investigator if Sponsor is in agreement.

Dosing will be terminated for any subject experiencing a serious device-related injury (see Section 12.14). For subjects experiencing a device failure or non-serious device-related injury, dosing may continue at the discretion of the investigator if the Sponsor is in agreement.

If study drug is to be terminated due to an SAE or serious device-related injury, dosing may be tapered off, rather than halted abruptly, at the investigator's discretion, so appropriate adjustments to GIR and/or alternative therapy for hypoglycemia can be initiated.

If possible, dosing should continue uninterrupted during the study, but interruption is permissible if necessary for the care of the patient e.g., a PET scan. Dosing should be resumed as soon as possible, following the same GIR weaning schedule as at initiation.

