9.3.3. Preparation, Dispensing and Administration

- CSI-Glucagon™ and vehicle will be supplied as 1 mL of non-aqueous solution in plastic Crystal Zenith (CZ) 2 mL vials. Each vial of CSI-Glucagon™ will be used to fill a single OmniPod® pump.
- CSI-Glucagon™ will be transferred to the OmniPod® using the kitted syringe and needle. Alternatively, a DMSO-compatible B Braun Injekt F® Low Waste Syringe 1 mL (supplied by Xeris) may be used along with the fill needle supplied by the pump manufacturer. If CSI Glucagon™ is not transferred into the OmniPod® within one hour of being drawn up into the syringe, the syringe, needle and drug should be discarded, and a fresh vial, needle and syringe should be used to fill the pod.

To maintain blinding during the randomized portion of the trial (Period 2), study medications will be blinded. The investigator will have the ability to unblind should such be necessary for the care of the subject in an emergency situation. During the open-label portion of the study (Period 3), study drug may be dispensed by any appropriately trained member of the study staff. During Period 3, dosing will be adjusted every 7 days as applicable based on the current body weight of the subject. During either period, the OmniPod® pump may be loaded with study drug by the pharmacist or other appropriately trained study staff.

The OmniPod® pump placement and study procedures will be performed by qualified/trained site staff who have read the OmniPod® Instructions for Use and following Table 3 for conversion of required glucagon flow rate to OmniPod® basal settings for pumping insulin.

Table 3: OmniPod® Controller Settings

Treatment	Desired Basal Rate	OmniPod® Setting	OmniPod® Setting (4 kg infant)
CSI-Glucagon™	2.5 µg/kg/hr	Infant weight in kg * 0.05 U/hr	0.2 U/hr
	5 µg/kg/hr	Infant weight in kg * 0.1 U/hr	0.4 U/hr
	10 µg/kg/hr	Infant weight in kg * 0.2 U/hr	0.8 U/hr
	15 µg/kg/hr	Infant weight in kg * 0.3 U/hr	1.2 U/hr
	20 µg/kg/hr	Infant weight in kg * 0.4 U/hr	1.6 U/hr

During Period 2 (blinded treatment), each OmniPod® will be used for a maximum of 48 hours. During period 3 (open-label), each OmniPod® will be used for up to 3 days, and will then be exchanged for a fresh pump. Before placement and after use each, each OmniPod will be weighed to the nearest whole mg (see Appendix 2).

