9.3.4. Device Reliability

A secondary objective of the study is to assess reliability of the OmniPod® infusion pump. This will be accomplished by performing weight-based estimates of dose volume delivery and noting episodes of significant infusion site leakage, device failures, malfunctions or occlusions.

Unless operational considerations at a site preclude it, all OmniPod® infusion pumps should be weighed before and after use, following the procedure outlined in Appendix 2. Given the short duration, the pump used for the 4-hour “switch out” at the beginning of Period 3 is excluded from this requirement.

If operational considerations make a site unable to weigh OmniPod® pumps, information on delivery volume obtained from the PDM should be captured in the EDC each time a pump is removed from a subject.

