 - b. If GIR cannot be reduced because glucose level is < 70 mg/dL (3.9 mmol/L), **restore continuous enteric feeding if that has been suspended**, or increase glucose infusion rate by 2 mg/kg/min and **increase study drug infusion rate by 5 µg/kg/hour (to a maximum of 20 µg/kg/hr)** and check blood glucose in 1 hour.
 10. If glucose is <50 mg/dL (2.8 mmol/L), give 200 mg/kg dextrose by IV push, increase GIR by 2 mg/kg/min, **increase study drug infusion rate by 5 µg/kg/hour (to a maximum of 20 µg/kg/hr)** and check blood glucose in 30 minutes. At 12 hours after start of study drug, determine average GIR since the start of blinded therapy, excluding the first 2 hours. If average “on treatment” GIR has been reduced by < 20% from the baseline value determined in Period 1, take the following actions:
 - a. Remove the pump and weigh it.
 - b. Replace the pump with a new one at the same flow rate setting as the previous pump and a fresh supply of the same blinded study drug.
 - c. Monitor POC glucose over the next 12 hours, adjusting GIR using the same rules as above for making IV fluid adjustments in the interim.

{Note: This same procedure should be followed if the pump alarms or if there is an acute deterioration in an otherwise stable subject, indicating a possible occlusion.}

Day 1

At 24 hours after the initial start of study drug, determine average GIR since the start of blinded therapy, excluding the first 2 hours. Then compare the “on treatment” GIR to the baseline value determined in Period 1 and calculate the percentage change. Depending on percentage change in GIR, follow the procedures under either item 1 or item 2.

1. At 24 hours if average GIR has been reduced by < 20% from the baseline value determined in Period 1, complete the following procedures:

- a. Draw blood for plasma insulin and glucagon levels as well as CBC and CMP.
 - b. Remove and weigh the OmniPod® pump (Appendix 2) and:
 - a. Photograph the application site, paying particular attention to the cannula insertion site.
 - o Assess site for edema and erythema using the Draize scale. Any Draize scores >0 should be followed to resolution, including a follow-up photograph.
 - c. Proceed to Period 3 (see 10.2.3).
2. At 24 hours if average GIR has been reduced by $\geq 20\%$ from the baseline value determined in Period 1, complete the following procedures:
- a. Continue to adjust the GIR during day 1 as per day 0.

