10.2.3. Period 3: Open-label Treatment

After 24 hours of the initial start of study drug, subjects with a reduction in average GIR <20% at 24 hours will be assigned to open-label CSI-Glucagon™.

After 48 hours of the initial start of study drug, subjects with a reduction in average GIR $\geq 20\%$ at 24 hours will be assigned to open-label CSI-Glucagon™.

After a subject is assigned to open-label CSI-Glucagon™, the following procedures will be performed.

Note: If continuous enteric feed was reduced in period 2 and increased feeding is necessary by the algorithm, the same rate as established during period 1 should be the target, and any additional demands will be covered with the IV GIR.

Period 3:

At the start of open-label treatment:

1. Photograph the site of approximate cannula insertion prior to application of a new OmniPod® pump.
2. Using the same procedures for loading and weighing the pump, and confirming cannula deployment as detailed for Day 0, apply a new OmniPod® pump containing CSI-

Glucagon™ (5 mg/mL), instruct the pump to insert the cannula and set basal rate of 5 µg/kg/hr. Record time of starting the pump; this is t=0.

3. Adjust IV fluids as per the Day 1 procedures.
4. At 4 hours, remove the OmniPod® pump and:
 - a. Photograph the application site, paying particular attention to the cannula insertion site.
 - b. Assess site for edema and erythema using the Draize scale. Any Draize scores > 0 should be followed to resolution, including a follow-up photograph.
5. The investigator should provide an assessment as to whether continued treatment would be helpful for clinical care.
 - a. If yes, and open-label treatment will be continuing, perform “real-world” pump change-out procedure (see Section 9.3.3).
 - b. If no, and open label treatment is ending, remove CGM and draw blood for immunogenicity testing, plasma insulin and glucagon levels as well as CBC, and CMP. Do not perform the “real-world” pump change-out procedure in this case.
6. If CSI-Glucagon™ treatment is considered helpful for clinical care, therapy may continue, including intermittently should procedures, e.g., PET scan, require temporary discontinuation, for up to a cumulative 28-day glucagon exposure.

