 - a. Using the same procedures for loading and weighing the pump, and confirming cannula deployment as detailed for Day 0, a new OmniPod® pump containing CSI-Glucagon™ solution should be placed immediately and again at least every 72 hours, including any time the pump alarms due to an occlusion.
 - b. Each time a pump is replaced, the safety of pump switch out procedures should be as assessed by occurrence of blood glucose < 50 mg/dL.
 - c. Each time a pump is removed, including at final termination of therapy, the pump should be weighed, and the placement site should be photographed and assessed with Draize scales and any reactions followed to resolution.
 - d. POC glucose will be assessed every three hours; or more frequently if the CGM shows glucose falling <70 mg/dL (3.9 mmol/L) or rising above >200 mg/dL (11.1 mmol/L). Additionally, the trajectory of change in plasma glucose concentration based on the two most recent POC measurements should be used to adjust the frequency of glucose monitoring as needed to prevent plasma glucose <70 mg/dL (3.9 mmol/L) or >200 mg/dL (11.1 mmol/L).
 - e. CGM will be utilized for rapid alerts, which will trigger POC assessments of blood glucose that will be used to guide clinical decisions. At least 2 hours prior to each planned pump change, confirm the CGM sensor is working and place another as needed.
 - f. Every 2 weeks during treatment, draw blood for immunogenicity testing.
7. Whenever CSI-Glucagon™ treatment is temporarily paused and when treatment ends:
 - a. Draw blood for CBC, CMP, immunogenicity testing and plasma insulin and glucagon.
 - b. Perform physical exam and measure height and weight.

- c. Resume IV fluids at pre-study rate and manage glucose as per standard procedures.

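### In Period 3 the 72-hour pump change interval can outlast the 5 mg fill once the infusion rate has been raised, and no earlier change is planned

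*Combined protocol and SAP*

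**What the plan says.** **Fill.** Section 9.3.1 gives 5 mg/mL in 1 mL vials. Section 9.3.3 adds: "Each vial of CSI-Glucagon™ will be used to fill a single OmniPod® pump". Period 3 pumps are loaded by the Day 0 procedure (Section 10.2.3), which is a 1 mL load.

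**Wear limit.** Section 9.3.3: "During period 3 (open-label), each OmniPod® will be used for up to 3 days, and will then be exchanged for a fresh pump". Under Section 10.2.3 a new pump "should be placed immediately and again at least every 72 hours, including any time the pump alarms due to an occlusion". The Synopsis gives the same 72 h interval. In Period 2 the maximum is 48 h per pump.

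**Rate.** Period 2 and Period 3 both start at 5 µg/kg/hr. Section 10.2.2 raises the rate in steps of 5 when glucose is low, up to 20 µg/kg/hr. For Period 3, Section 10.2.3 says "Adjust IV fluids as per the Day 1 procedures", and the Day 1 text says "Continue to adjust the GIR during day 1 as per day 0". The Synopsis describes the start of Period 3 "with hourly POC glucose measurements and fluid adjustments as per Period 2". Section 10.2.3 states the 5 µg/kg/hr setting for the first open-label pump and gives no rate for later ones.

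**Tracking of volume.** Sites that cannot weigh pumps are told that "information on delivery volume obtained from the PDM should be captured in the EDC each time a pump is removed from a subject". Appendix 2 also takes the PDM reading after the pump has come off.

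**Continuity.** Section 7.2: "If possible, dosing should continue uninterrupted during the study". Pauses are allowed where the infant's care needs them.

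**The concern.** The fill is fixed, but consumption rises with both rate and body weight, while the change interval depends on neither. If the rate is high enough and the infant heavy enough, a pump kept for the full 72 h has nothing left to deliver at the end. The text sets no planned change by volume, rate or weight. The delivered volume is recorded only at removal, too late to schedule a change. The replacement trigger written for Period 3 is an occlusion alarm. Section 10.2.2 has a wider note for Period 2, covering any pump alarm or a sudden worsening, but whether it carries over is not stated.

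At stake is an unplanned stop in glucagon for an infant who needed escalation to hold glucose, which is contrary to the intent of Section 7.2.

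**Working it through.** **Inputs.** Concentration 5 mg/mL and 1 mL vial (9.3.1); one vial per pump (9.3.3); maximum 20 µg/kg/hr (10.2.2); change interval 72 h (Synopsis, 9.3.3, 10.2.3); eligible weight above 2.3 kg with no upper limit, age under 12 months (8.1, 8.2). Drug per pump is at most 1 mL × 5 mg/mL = 5000 µg.

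**Step 1: reproduce Table 3.** A 4 kg infant at 20 µg/kg/hr receives 80 µg/hr, and 80/5000 = 0.016 mL/hr. Table 3 gives 1.6 U/hr, which corresponds to 100 U per mL. On that conversion all five 4 kg settings (0.2, 0.4, 0.8, 1.2 and 1.6 U/hr) reproduce exactly.

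**Step 2: run-out for that infant.** Run-out (h) = 5000/(rate × kg) = 5000/80 = 62.5 h, and 72 − 62.5 = 9.5 h. In Table 3 units, 72 h needs 72 × 1.6 = 115.2 U against 100 U. At 15 µg/kg/hr it needs 72 × 1.2 = 86.4 U, which is covered, as are the lower rates.

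**Step 3: weight above which 72 h exceeds the fill.** Limit (kg) = usable µg/(72 × rate). The priming volume is not given, so a loss of 0.1 mL (500 µg) is shown as an assumption.

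| Rate (µg/kg/hr) | No priming loss | 0.1 mL lost (assumed) |
|---|---|---|
| 20 | 5000/1440 = 3.5 kg | 4500/1440 = 3.1 kg |
| 15 | 5000/1080 = 4.6 kg | 4500/1080 = 4.2 kg |
| 10 | 5000/720 = 6.9 kg | 4500/720 = 6.3 kg |
| 5 | 5000/360 = 13.9 kg | 4500/360 = 12.5 kg |

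With the same assumed loss, the 4 kg infant at 20 runs out at 4500/80 = 56.3 h.

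**Step 4: does it depend on the rate carrying over between pumps?** Suppose every later pump restarted at 5 and was stepped up hourly to 20. Use by 72 h is 5 + 10 + 15 + 20 × 69 = 1410 µg/kg, so the limit is 5000/1410 = 3.5 kg. The 4 kg infant has 5000/4 = 1250 µg/kg available and empties at 3 + (1250 − 30)/20 = 64 h, still 8 h short. The result barely changes.

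**Step 5: Period 2, 48 h limit.** At a constant 20 the limit is 5000/(20 × 48) = 5.2 kg. With hourly steps from 5, use is 5 + 10 + 15 + 20 × 45 = 930 µg/kg, and the limit is 5000/930 = 5.4 kg. The lower figure is the bound: Section 9.1 lets the starting rate be adjusted, and Section 10.2.2 rechecks at 30 minutes after glucose below 50 mg/dL, so steps can come faster than hourly.

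**The case against.** The best defence is that nothing in the plan is miscalculated. The protocol never says that 1 mL lasts 72 h. The interval is a ceiling, and a site that changes a pump at 50 h complies. That stands: what is missing is a rule, not a correct figure.

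The exposed group is also limited. At 5 µg/kg/hr the fill covers 72 h up to 13.9 kg. The 4 kg infant falls short at only one of the five Table 3 rates, and at 10 µg/kg/hr the infant must weigh more than 6.9 kg. High rates reach Period 3 through cross-references and not through a direct statement. That reading is reasonable, but it is an inference.

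The safeguards are real. Subjects are in-patients, POC glucose is checked at least every 3 hours, and CGM gives rapid alerts. Each algorithm step up in drug comes with a 2 mg/kg/min rise in GIR, in Period 3 as in Period 2. Later weaning may lower the GIR again, so IV cover at run-out cannot be known. These measures limit harm, but CGM and POC glucose respond only after glucose has begun to fall.

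A reader might infer that infants would be left without glucagon unnoticed. The documents do not support that. Staff must have read the OmniPod Instructions for Use, which are not among the documents, and how a low or empty reservoir is signalled is not described.

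A reader might also infer a threat to the efficacy result. Period 3 does not feed the primary endpoint. In Period 2 the problem needs more than about 5.2 kg and sustained high rates, any pump alarm already calls for replacement, and a gap in active drug would count against the drug.

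**Conclusion.** The concern holds as a patient-safety gap, mainly in Period 3. After escalation, the stated fill, maximum rate and change interval together allow a pump to stop delivering before its planned change. This occurs above about 3.5 kg at 20 µg/kg/hr, 4.6 kg at 15 and 6.9 kg at 10. For the protocol's own 4 kg infant at 20, the shortfall is up to 9.5 h if the pump is not replaced sooner. Period 2 is a secondary concern.

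These figures assume a constant rate over the pump's life, a full 1 mL fill and no priming loss; any loss lowers the limits. The documents give neither a weight distribution nor the share of infants reaching 10 to 20 µg/kg/hr, so frequency is unknown. The arithmetic is certain, but the clinical consequence is not shown. The point does not call Table 3 or the primary analysis into question. It is a cheap improvement that should be made.

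**What to change.** In Sections 9.3.3 and 10.2.3, and in 10.2.2 identically for both arms, state that the pump is changed at the earlier of:

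- the wear limit (48 h in Period 2, 72 h in Period 3), or
- before the calculated run-out of 5000/(rate × kg) hours, less a stated priming allowance.

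Recalculate whenever the rate or dosing weight changes, using the drug still in the pump. In Section 10.2.3, widen the replacement trigger from occlusion alarms to any pump alarm. Because the rule uses only the rate setting and the weight, it can be applied in Period 2 without unblinding.

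**Cost.** One sentence in three sections, plus some extra pumps and vials. For 28 days (672 h) constantly at 20 µg/kg/hr and before priming loss, 72 h changes need 672/72 = 9.3, so 10 pumps. At 4 kg the rule needs 672/62.5 = 10.8, so 11. At 6 kg a fill lasts 5000/120 = 41.7 h, and 672/41.7 = 16.1, so 17. Each extra change also means a new cannula insertion, weighing, photographs, Draize scoring and a CGM check. No change is added where the fill, less the priming allowance, already covers the wear limit.

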9.3.4. Device Reliability

A secondary objective of the study is to assess reliability of the OmniPod® infusion pump. This will be accomplished by performing weight-based estimates of dose volume delivery and noting episodes of significant infusion site leakage, device failures, malfunctions or occlusions.

Unless operational considerations at a site preclude it, all OmniPod® infusion pumps should be weighed before and after use, following the procedure outlined in Appendix 2. Given the short duration, the pump used for the 4-hour “switch out” at the beginning of Period 3 is excluded from this requirement.

If operational considerations make a site unable to weigh OmniPod® pumps, information on delivery volume obtained from the PDM should be captured in the EDC each time a pump is removed from a subject.

9.3.5. Drug Storage and Drug Accountability

Unless notified otherwise by the Sponsor, all supplied CSI-Glucagon™ and control vials are to be stored at controlled room temperature between 20°C to 25°C (68° to 77°F), and should be clear and of a water-like consistency at time of use.

The investigator or an approved study staff will ensure that the study medications are stored in a secure area under recommended storage conditions and in accordance with applicable regulatory requirements.

The site will maintain appropriate documentation of continuous storage conditions and these records will be monitored, on an on-going basis by the Xeris or its representative. Any deviations in the storage conditions must be documented (including minimum and maximum temperature excursions, as well as estimate of total duration outside the recommended storage conditions). Such deviations must be communicated to the Sponsor as soon as identified by the site with appropriate course of action taken regarding the future use of the study medications upon consultation with Xeris Pharmaceuticals.

The investigator must maintain adequate records documenting the receipt, use, loss or other disposition of the investigational drug products and supplies, including OmniPods, and will return unused products to Xeris at the end of the study, following directions from Xeris.

